**Table 6-15: Dose modification for non-hematological, non-neurological toxicity**

Prior to Dosing (Day 1 or Day 15)	Toxicity		Dose level for subsequent cycles	
If diarrhea remains $\geq$ Grade 2 after 2 weeks, discontinue treatment.		colostomy output; limiting self-care ADL		
	4	Life threatening consequences; urgent intervention indicated	Reduce 1 dose level	Reduce 1 dose level of iv bolus and infusion
	CTCAE (V5.0) Toxicity Grade	Stomatitis/Mucositis	Oxaliplatin	5-Fluorouracil
If stomatitis $\geq$ Grade 2 on Day 1 or Day 15, hold treatment. Perform weekly assessments. If stomatitis $<$ Grade 2 within 2 weeks, proceed with treatment at a dose level according to the highest Grade experienced. If stomatitis remains $>$ Grade 2 after 2 weeks, discontinue treatment.	1	Minimal symptoms with normal oral intake	Maintain dose level	Maintain dose level
	2	Moderate pain, analgesics indicated; altered oral intake	Maintain dose level	Maintain dose level
	3	Severe pain; unable to adequately aliment or hydrate orally	Maintain dose level	Reduce 1 dose level of iv bolus and infusion
	4	Life-threatening consequences, urgent intervention indicated	Reduce 1 dose level	Reduce 1 dose level of iv bolus and infusion

ADL=activities of daily living; CTCAE= Common Terminology Criteria for Adverse Events; iv=intravenous(ly)

This document cannot be used to support any application and any extension of any variation of the product. It is the property of UCB and is supplied under the terms of the Clinical Study Agreement. It is supplied for the use of the clinical investigator and the clinical trial participants only. It is not to be distributed outside the clinical trial.

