**Table 6-14: Dose modification for hematological toxicity**

Prior to Dosing (Day 1 or Day 15)	Toxicity		Dose level for subsequent cycles	
	CTCAE (V5.0) Toxicity Grade	ANC (x10  /L)	Oxaliplatin	5-Fluorouracil
If ANC <1.2 on Day 1 or Day 15, hold treatment and perform weekly blood counts.	1	≥1.2	Maintain dose level	Maintain dose level
	2	1.0 to <1.2	Maintain dose level	Maintain dose level
	3	0.5 to <1.0	Reduce 1 dose level	Maintain dose level

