**Table 6-14: Dose modification for hematological toxicity**

Prior to Dosing (Day 1 or Day 15)	Toxicity		Dose level for subsequent cycles	
	CTCAE (V5.0) Toxicity Grade	Platelets ( $\times 10^9/L$ )	Oxaliplatin	5-Fluorouracil
If ANC is $\geq 1.2$ within 2 weeks, proceed with treatment at a dose level according to the lowest ANC result of the delayed weeks.	4	<0.5	Reduce 1 dose level	Omit iv bolus and reduce infusion 1 dose level
If ANC remains <1.2 after 2 weeks, discontinue treatment.				
If platelets <75 on Day 1 or Day 15, hold treatment. Perform weekly blood counts.	1	$\geq 75$	Maintain dose level	Maintain dose level
If platelets $\geq 75$ within 2 weeks, proceed with treatment at a dose level according to the lowest platelets result of the delayed weeks.	2	50 to <70	Maintain dose level	Maintain dose level
If platelets remain <75 after 2 weeks, discontinue treatment.	3	10 to <50	Reduce 1 dose level	Maintain dose level
	4	<10	Reduce 2 dose levels	Maintain dose level

ANC=absolute neutrophil count; CTCAE= Common Terminology Criteria for Adverse Events; iv=intravenous(ly)

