**Table 6-15: Dose modification for non-hematological, non-neurological toxicity**

Prior to Dosing (Day 1 or Day 15)	Toxicity		Dose level for subsequent cycles	
	CTCAE (V5.0) Toxicity Grade	Diarrhea	Oxaliplatin	5-Fluorouracil
If diarrhea $\geq 2$ on Day 1 or Day 15, hold treatment. Perform weekly assessments.	1	Increase of <4 stools/day, or mild increase in colostomy output	Maintain dose level	Maintain dose level
If diarrhea is <Grade 2 within 2 weeks, proceed with treatment at a dose level according to the highest Grade experienced.	2	Increase of 4 to 6 stools/day, or moderate increase in colostomy output; limiting instrumental ADL	Maintain dose level	Maintain dose level
	3	Increase of $\geq 7$ stools/day; hospitalization indicated; severe increase in	Maintain dose level	Reduce 1 dose level of iv bolus and infusion

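### In Part C, stomatitis that stays at exactly Grade 2 for two weeks meets neither the proceed nor the discontinue condition in Table 6-15, so the mFOLFOX6 hold has no end point

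*Protocol*

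**What the plan says.** Protocol Section 6.6.3.4.3 and Table 6-15 give the mFOLFOX6 rules for non-hematological, non-neurological toxicity in Part C. For stomatitis or mucositis there are three statements:

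- Hold: "If stomatitis $\geq$ Grade 2 on Day 1 or Day 15, hold treatment", with weekly assessments.
- Proceed: "If stomatitis $<$ Grade 2 within 2 weeks, proceed with treatment at a dose level according to the highest Grade experienced".
- Stop: "If stomatitis remains $>$ Grade 2 after 2 weeks, discontinue treatment".

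The diarrhoea rule in the same table has the same three steps:

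- Hold: "If diarrhea $\geq 2$ on Day 1 or Day 15, hold treatment".
- Proceed: "If diarrhea is <Grade 2 within 2 weeks, proceed with treatment", at a dose level set by the worst grade.
- Stop: "If diarrhea remains $\geq$ Grade 2 after 2 weeks, discontinue treatment".

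Table 6-14 follows the same pattern for blood counts. For neutrophils, the hold is "If ANC <1.2 on Day 1 or Day 15, hold treatment and perform weekly blood counts" and the stop is "If ANC remains <1.2 after 2 weeks, discontinue treatment"; treatment proceeds once ANC is at or above 1.2. For platelets, the hold and stop limits are both below 75, and treatment proceeds at 75 or above.

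**The concern.** A hold-and-review rule should send every held participant to one outcome when the review period ends. The stomatitis rule does not. Grade 2 is high enough to start the hold and too high to end it by proceeding, but not high enough to end it by stopping.

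A site with such a participant could leave the hold open, stop the chemotherapy on its own judgement, or restart although the proceed limit is not met. The choice has consequences elsewhere in the protocol:

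- Section 6.6.3.4 considers continued UCB6114 for participants who permanently discontinue all or part of mFOLFOX6 for toxicity. Without a stop decision, it is unclear when a participant enters that group.
- Section 10.3.1 tabulates adverse events leading to temporary interruption or reduction separately from those leading to discontinuation. The same clinical course could be counted in either table, depending on the site.

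**Working it through.** No figure in the protocol is at issue, so the check is one of logical coverage: after a hold, does every possible state at two weeks meet exactly one of the proceed and stop conditions? The limits below come from Tables 6-14 and 6-15.

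| Rule | Hold | Proceed within 2 weeks | Stop after 2 weeks | State left over |
|---|---|---|---|---|
| Stomatitis | Grade ≥2 | Grade <2 | Grade >2 | Grade 2 |
| Diarrhoea | Grade ≥2 | Grade <2 | Grade ≥2 | none |
| ANC (×10⁹/L) | <1.2 | ≥1.2 | <1.2 | none |
| Platelets (×10⁹/L) | <75 | ≥75 | <75 | none |

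Stomatitis grade by grade at two weeks: Grades 0 and 1 proceed, Grades 3 and 4 stop, and Grade 2 does neither. Of the grades that can trigger the hold (2, 3 and 4), one of three has no outcome.

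The platelet comparison holds for these three limits only. The platelet dose-level bands in Table 6-14 have their own gap: Grade 1 is 75 or more and Grade 2 is 50 to below 70, so a lowest count of 70 to below 75 triggers a hold but has no listed dose level on restart.

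Next, does other text close the stomatitis gap?

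- **Grade 2 row of Table 6-15.** It keeps the dose level unchanged for both drugs. That sets the dose once treatment proceeds, not whether it may proceed.
- **Sections 6.6.3.2 and 7.1.4.** These allow suspension for up to 3 weeks until toxicity is Grade 2 or less. They govern UCB6114, with a different window and limit, and say nothing on mFOLFOX6.
- **Section 7.1.3.** It provides for discontinuation for unacceptable toxicity in general terms, with no grade or time limit that would settle this case.

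None supplies a decision for mFOLFOX6 at persistent Grade 2.

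Finally, does the gap reach the DLT Evaluable Set? Section 10.1 requires at least 80% of planned mFOLFOX6 during the DLT assessment period. Section 4.1.5.2.1 sets that period as Days 1 to 28 of Cycle 1, and Table 1-8 starts mFOLFOX6 on Days 1 and 15. A missed Day 15 dose leaves 1/2 = 50% of planned administrations, below 80%. But a hold that starts on Day 15 reaches two weeks on Day 15 + 14 = Day 29, after the period has closed. The Day 15 dose is lost through the hold, which is unambiguous. If the visit falls at the early edge of the ±2-day window, two weeks is Day 13 + 14 = Day 27. Even then, neither a continued hold nor a stop supplies the dose, and a restart at Grade 2 is outside the written proceed limit.

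**The case against.** The strongest reply is that the participant is not without instruction. The cell orders a hold with weekly assessments, and with neither exit condition met that hold stays in force. Section 6.6.3.4.3 presents the table as recommendations, and Section 7.1.3 still allows discontinuation for unacceptable toxicity. This stands in part: what is missing is not all guidance but a proceed-or-stop decision at two weeks, and hence an end to the hold. Calling the table a recommendation does not help, because it makes none for this state.

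It can also be said that this is probably a one-symbol slip, given the parallel diarrhoea wording, or a symbol lost when the PDF was read. A reading error cannot be fully excluded. However, the greater-or-equal sign was read correctly in the hold statement of the same cell and in the diarrhoea stop rule, so the text is taken as it stands. A slip would still need correcting.

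A reader might infer more: that the gap decides who is evaluable for DLT, and so feeds into the mTPI escalation decisions. The documents do not support that. The shortfall against 80% comes from the hold, and at the scheduled timing the two-week decision falls after the DLT window.

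**Conclusion.** The stomatitis stop limit in Table 6-15 does not fit its own hold and proceed limits, and it departs from the single-limit pattern of the diarrhoea, ANC and platelet rules. Persistent Grade 2 stomatitis is left on a hold with no end point.

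The size is small. It concerns one grade of one toxicity, for background chemotherapy in one study part. What can vary between sites is the mFOLFOX6 received and whether the event is tabulated as an interruption or a discontinuation. As a scale, Part C enrolls up to 27 participants, with 3 to 9 per dose level, so one participant classified differently is 1/27 = 3.7% of the part at full enrollment and 1/9 = 11.1% to 1/3 = 33.3% of a dose level. How often this would happen cannot be estimated from the protocol. No effect is shown on the DLT Evaluable Set, dose escalation, sample size or any error rate.

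The conclusion assumes that the symbols in the table are as printed and that no document outside the protocol gives sites a further instruction. Severity: minor.

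**What to change.** Reconcile the hold, proceed and discontinue limits for stomatitis in Table 6-15 so that every grade at two weeks leads to exactly one action. Which action applies to persistent Grade 2 is for the sponsor's clinical team; the parallel diarrhoea rule shows the structure but does not settle the clinical choice. The text change is one symbol or one sentence and can go into the next protocol amendment. The platelet bands in Table 6-14 (70 to below 75) can be reconciled in the same pass.

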## **6.7 Criteria for study hold or dosing stoppage**

Detailed procedures for reporting SAEs and other safety events (including Rapid Alert Procedures) that may meet study or individual study part hold criteria are provided in Appendix 6 (Section 11.6).

The study or individual study part will be immediately suspended (ie, any participant who has not received dose(s) of UCB6114 at the time of study/study part suspension will not be administered UCB6114) if 1 or more study participants develop any of the following AEs deemed to be at least possibly related to UCB6114 administration by the investigator and the sponsor:

- Death
- Life-threatening organ failure requiring intervention to prevent death or permanent disability (eg, respiratory failure requiring ventilation, renal failure requiring dialysis, heart failure requiring hemodynamic support).

The SMC will be consulted for both study/study module suspension and potential restart (details can be found in the SMC charter).

The management of ongoing participants may be discussed on an individual basis with the investigator and the participants taking into account the benefit/ risk assessment, unless asked by the SMC and/or a regulatory authority/ies not to do so.

Enrolment of new participants into the study or individual study module will not be restarted until:

- Sponsor and the SMC have agreed a risk mitigation strategy which meets the requirements of any regulatory authority/ies to whom details of the AE have been submitted, and
- Based on local policies, the Independent Ethics Committees (IECs)/Institutional Review Boards (IRBs) have been notified, and
- Where applicable, regulatory authorities have been notified and have approved a substantial amendment for study restart.

## **6.8 Treatment after the end of the study**

The planned duration of study treatment is 2 cycles. Participants may, however, remain on study for additional cycles if they are receiving therapeutic benefit (SD, PR, or CR) or until they fulfill one of the criteria for study discontinuation. Upon discontinuation of treatment, participants will be referred to appropriate follow-up care per the investigator's judgment.

# **7 DISCONTINUATION OF STUDY MEDICATION AND PARTICIPANT DISCONTINUATION/WITHDRAWAL**

## **7.1 Discontinuation of study medication**

The IMP will be discontinued if any of the stopping criteria are met or if the participant is withdrawn from the study (see Section 7.2).

### 7.1.1 Liver Chemistry Stopping Criteria

The threshold of laboratory abnormalities for a potential case of drug-induced liver injury depends on the participant's individual baseline values and underlying conditions. Participants who present with the following laboratory abnormalities should be evaluated further to definitively determine the etiology of the abnormal laboratory values:

- Participants with AST or ALT and total bilirubin baseline values within the normal range who subsequently present with AST or ALT  $\geq 3\times\text{ULN}$  concurrent with a total bilirubin  $\geq 2\times\text{ULN}$ .
- For participants with pre-existing ALT OR AST OR total bilirubin values above the ULN, the following threshold values should be used in the definition mentioned above:
  - For participants without liver metastases: AST or ALT value  $\geq 2$  times the baseline values *AND*  $\geq 3\times\text{ULN}$
  - For participants with liver metastases: AST or ALT value  $\geq 2$  times the baseline values *AND*  $\geq 8\times\text{ULN}$

Concurrent with

- For participants with preexisting values of total bilirubin above the normal range: Total bilirubin  $\geq 2$  times the baseline values OR if the value reaches  $\geq 3\times\text{ULN}$  (whichever is lower).

The participant should return to the investigational site and be evaluated as soon as possible, preferably within 24 hours from awareness of the abnormal results. This evaluation should include laboratory tests, detailed history and physical assessment, and the possibility of hepatic neoplasia (primary or secondary) should be considered. In addition to repeating measurements of AST and ALT, laboratory tests should include albumin, creatine kinase, total bilirubin, direct and indirect bilirubin, gamma-glutamyl transferase, prothrombin time/international normalized ratio, and ALP. A detailed history, including relevant information, such as review of ethanol, acetaminophen, recreational drug and supplement consumption, family history, occupational exposure, sexual history, travel history, history of contact with a jaundiced person, surgery, blood transfusion, history of liver or allergic disease, and work exposure, should be collected. Further testing for acute hepatitis A, B, or C infection and liver imaging (eg, biliary tract) may be warranted. All cases confirmed on repeat testing as meeting the laboratory criteria defined above, with no other cause for liver function test abnormalities identified at the time should be considered potential Hy's Law cases irrespective of availability of all the results of the investigations performed to determine etiology of the abnormal liver function tests. Such potential Hy's Law cases should be reported as SAEs.

Interruption of the study medication should be considered by the investigator when a participant meets one of the conditions outlined above.

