### 7.1.2 QTc Stopping Criteria

A participant who meets either bulleted criterion based on the average of triplicate ECG readings will be withdrawn from study medication.

- QTc  $>500\text{msec}$  OR Uncorrected QT  $>600\text{msec}$

- Change from baseline of QTc >60msec

For participants with underlying bundle branch block, follow the discontinuation criteria listed in **Table 7-1**.

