### 7.1.3 Other criteria for discontinuation of study medication

Participants must discontinue study treatment if they experience any of the following:

1. There is confirmation of a pregnancy during the study, as evidenced by a positive pregnancy test.
2. The participant experiences unacceptable toxicity.
  - For information on dose delays due to drug-related toxicity, see Section [6.6.1](#) (Part A and Part A1), Section [6.6.2](#) (Part B), and Section [6.6.3](#) (Part C). Participants will discontinue treatment, unless, in the opinion of the investigator, they are experiencing clinical benefit and it is in their best interest to continue treatment. For these participants, treatment may continue at a reduced dose at the discretion of the investigator and Sponsor.
3. The participant has documented evidence of progressive disease.
  - Participants with progressive disease before the end of Cycle 1 may be discontinued from study medication at the discretion of the investigator. Participants with progressive disease beyond Cycle 1 will be discontinued from study medication. In cases where progression is not clear and, in the opinion of the investigator, the participant may be having clinical benefit, the participant may continue treatment, but must be reimaged within 2 cycles of treatment.
4. The participant, for any reason, requires treatment with another therapeutic agent or modality for his/her cancer (with the exception of palliative bone-directed radiotherapy). In this case, discontinuation from the study treatment must occur before introduction of the new agent or modality.

---

5. Participant takes prohibited concomitant medications as defined in this protocol.

Participants who discontinue the study medication and/or study early will have end-of-study (SFU) procedures performed as shown in the Schedules of Activities for Part A ([Table 1-4](#)), Part A1 ([Table 1-5](#) and [Table 1-6](#)), Part B ([Table 1-7](#)), and Part C ([Table 1-8](#)).

See the Schedules of Activities for Part A ([Table 1-4](#)), Part A1 ([Table 1-5 and Table 1-6](#)), Part B ([Table 1-7](#)), and Part C ([Table 1-8](#)) for data to be collected at the time of study treatment discontinuation and follow-up and for any further evaluations that need to be completed.

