#### **7.1.4        Temporary discontinuation of study medication**

A treatment dose may be withheld if a participant experiences toxicity as described in Section [6.6.1.2](#) (Part A), Section [6.6.1.3](#) Part A1), Section [6.6.2.2](#) (Part B), and Section [6.6.3.1](#) (Part C).

Participants who fail to receive the second planned dose of UCB6114 within 7 days of the scheduled administration day during the DLT Observation Period for reasons not related to toxicity will be replaced by a new participant in that cohort.

Treatment with UCB6114 may temporarily be suspended for up to 3 weeks beyond the scheduled treatment day until toxicities are resolved to CTCAE Grade 2 or less. If UCB6114 is held for more than 3 weeks beyond the scheduled treatment day, then the participant will be discontinued from treatment and will be followed up for safety per schedule of assessment.

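### Section 7.1 makes stopping the drug mandatory at any stopping criterion, but the liver stopping criteria in 7.1.1 only ask the investigator to consider interruption, so the default at those values is not fixed

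*Protocol*

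**What the plan says.** Protocol Section 7.1 opens with an unconditional rule on study drug: "The IMP will be discontinued if any of the stopping criteria are met". Three subsections follow with the criteria.

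- **7.1.1, liver chemistry.** The thresholds are introduced as triggers for investigation: "Participants who present with the following laboratory abnormalities should be evaluated further to definitively determine the etiology of the abnormal laboratory values". With normal baseline values, the trigger is AST or ALT at least 3×ULN together with total bilirubin at least 2×ULN. Adjusted limits apply when baseline values are raised, with a separate transaminase limit when liver metastases are present. A case confirmed on repeat testing, with no other cause identified at the time, is a potential Hy's Law case. The added duty for it is "Such potential Hy's Law cases should be reported as SAEs". The only sentence on dosing comes last: "Interruption of the study medication should be considered by the investigator when a participant meets one of the conditions outlined above".
- **7.1.2, QTc.** A participant meeting a criterion "will be withdrawn from study medication".
- **7.1.3.** This is headed "Other criteria for discontinuation of study medication" and lists five items, none of which names the liver thresholds.

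Appendix 2 (Section 11.2), note 1, again calls the 7.1.1 rules stopping criteria and sends the reader there for what has to be done. It speaks of both stopping and monitoring events without saying which liver result is which.

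**The concern.** A site holding a result above the 7.1.1 thresholds needs to know whether the next dose is given. Section 7.1 answers that the drug is discontinued; 7.1.1 leaves it to the investigator. Both are in force and neither yields to the other.

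This is a multicenter, first-in-human trial, so there is little prior human experience to guide judgment on hepatic risk. Two sites could each follow the protocol and treat identical laboratory values in opposite ways, and either could be recorded as deviating from it. Participants with possible drug-induced liver injury would be handled according to which sentence the site read.

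**Working it through.** No arithmetic applies: the protocol states no figure on this point and gives no incidence of threshold events. The check is to follow one participant through every rule that could settle the dosing question.

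Take normal baseline liver values, then ALT at least 3×ULN with total bilirubin at least 2×ULN.

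| Section | What it requires at these values | Does it fix the dosing default? |
|---|---|---|
| 7.1 | Discontinue | Yes: stop |
| 7.1.1 | Prompt evaluation; consider interruption | Yes: discretion, contradicting 7.1 |
| 7.1.1, confirmed case with no other cause found at the time | SAE reporting in addition | Nothing beyond the same discretion |
| 9.2.6 | Report to the sponsor within 24 hours if ALP is below 2×ULN and there is no alternative explanation | No: reporting only |
| 7.1.3 item 2 | Stop for unacceptable toxicity, with an exception for benefit | No: general |
| 7.1.4 | A hold is permitted until Grade 2 or less; stop if held too long | No: permissive and general |
| 7.2 item 3 | Withdraw if the investigator judges it best, including for a significant laboratory value | No: discretionary |
| DLT rules (4.1.2.4, 4.1.4.2.1, 4.1.5.2.1) | Count qualifying related Cycle 1 toxicity | No: they serve dose-level and schedule decisions |
| 6.6.2.2 and 6.6.3.2 | Stop for related Grade 4 nonhematologic toxicity | No: Parts B and C only, not tied to these thresholds |
| 6.7 | Suspend the study or part for related death or life-threatening organ failure | No: a later and more severe event |

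Four details matter.

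1. Confirmed cases are by definition cases that meet the laboratory conditions, so the interruption sentence reaches them too. What is missing is any stronger action for them.
2. The exception in 7.1.3 item 2 reads "Participants will discontinue treatment, unless, in the opinion of the investigator, they are experiencing clinical benefit", so even that rule can end in continued dosing.
3. The firm limb of 7.1.4 is "If UCB6114 is held for more than 3 weeks beyond the scheduled treatment day, then the participant will be discontinued from treatment". It operates only once someone has chosen to hold.
4. Meeting a DLT definition does not itself stop the participant: in Part A, 6.6.1.2 allows continued therapy with dose adjustment after a DLT.

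One could reconcile the texts as interrupting at discretion during work-up and stopping once the case is confirmed. That would be sensible, but no section says it. Redaction does not explain the gap, since the 7.1.1 text is continuous.

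**The case against.** The strongest reply is that 7.1.1 is the specific text and should prevail over a generic opening sentence and a heading. Its content is consistent throughout: evaluate, repeat, report, consider interruption. There are good reasons for discretion. The thresholds depend on baseline values and underlying conditions, hepatic neoplasia must be considered, and 9.2.6 accepts liver metastases as a possible alternate etiology. Nor is discretion confined to the liver rules: 7.1.3 items 2 and 3 contain it, and the text after the QTc criteria leaves other clinically significant ECG findings to physician judgment. So the firmer QTc wording does not by itself show that the liver wording is a mistake.

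Much of this stands. It explains why the sponsor might want discretion, and a mandatory hold is a clinical choice that nothing in the protocol compels. It does not remove the conflict. Section 7.1 has no exception for liver chemistry, Appendix 2 repeats the stopping label, and the 7.1.3 heading implies that the preceding subsections are discontinuation criteria. If discretion is intended, 7.1 and the 7.1.1 heading are wrong as written.

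A reader might also infer that a participant with a marked liver signal could be re-dosed without anyone looking. The protocol does not support that. Chemistry results should be available for review before infusion (9.1.5), immediate safety concerns go to the sponsor (Section 9), and 9.2.6 sets 24-hour reporting at the same 3×ULN and 2×ULN values, with an added ALP condition.

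**Conclusion.** The inconsistency holds. At the 7.1.1 thresholds the protocol gives two incompatible dosing instructions, does not say which governs, and adds no stronger dosing action for confirmed potential Hy's Law cases. Its practical size cannot be quantified, because no frequency of such cases is given. The surrounding safeguards make an unreviewed dose unlikely but leave the default open between stop, hold and continue. It should be corrected because it is a participant-level safety rule and belongs in the protocol rather than in an analysis plan.

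Two stronger conclusions are tempting and should be avoided. One is that 7.1.1 is silent on dosing for confirmed cases; it is not, since its interruption sentence covers them. The other is that confirmation on repeat testing should itself trigger permanent discontinuation. Section 7.1.1 classifies cases on causes known at the time, before all results need be available, so a participant could be stopped for good before hepatitis tests or imaging return. Permanent discontinuation has to wait for the completed work-up.

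**What to change.** Replace the last sentence of 7.1.1 with:

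> *IMP will be withheld when the thresholds above are met, pending repeat testing and etiologic work-up; it will be permanently discontinued if the abnormality is confirmed and the completed work-up identifies no other cause; if another cause (eg, liver metastases) is established, dosing may resume per Section 7.1.4.*

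Amend 7.1 so that discontinuation applies *as specified in Sections 7.1.1 to 7.1.3*, and align Appendix 2 note 1, including which liver result is a stopping event and which a monitoring event.

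The cost is one replaced sentence and two small alignments, with no extra data collection. The clinical downside is that some participants with metastasis-related abnormalities will have a dose delayed during work-up.

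If the sponsor prefers to keep discretion, the minimum is to except 7.1.1 from the mandatory sentence in 7.1 and to retitle 7.1.1, so that one instruction governs.
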